## **Our Specific Aims are:**

1. “Determination of the Influence of AET+ on PWC in Patients with ILD”.  
Specific Hypothesis: AET+ will improve measures of PWC, including our main outcome variable 6MWT distance, and peak WR, as well as performance and perceived fatigability over controls.  
*“Sub-study On Crossover:”* After completing the education-only regimen and subsequently completing the AET regimen, improvements similar to AET+ will be observed in 6MWT distance, peak WR, and fatigability.
2. “Characterization of the Cardiorespiratory Adaptation to AET in Patients with ILD.”  
Specific Hypothesis: After AET+, significant increases in AT-time and muscle oxygenation will be observed over control.  
*“Sub-study On Crossover:”* After completing the education-only regimen and subsequently completing the AET regimen, improvements similar to AET+ will be observed in AT-time and muscle oxygenation capacity.
3. Determination of the Influence of AET on Patient-reported Measures of Fatigue, Physical Activity, and Other HRQoL Domains in Patients with ILD.”  
Specific Hypothesis: After AET+, patients will report decreased fatigue severity measured by the Fatigue Severity Scale, increased physical activity measured by the Human Activity Profile, and improvement in other HRQoL domains measured by the St. Georges Respiratory Questionnaire and SF-36v2 over control.  
*“Sub-study On Crossover:”* After completing the education-only regimen and subsequently completing the AET regimen, improvements similar to AET+ will be observed in fatigue severity, physical activity and other HRQoL domains.
4. “One-year Follow Up on Hospitalization, Lung transplant, and Mortality.”  
This is a descriptive analysis to examine health outcomes of frequency, length and severity of hospitalizations, acceptance onto a lung transplant waiting list, and mortality occurring over the year after completion of the main study.

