- 3.2. After AET+, participation in physical activity will be increased over control.
- 3.3. After AET+, overall mood will be increased over control.
- 3.4 After AET, general HRQoL and HRQoL specific to ILD and IPF will all be improved over control.
- 3.5 In the Sub-study on Crossover we hypothesize that AET will result in improvements over baseline in all of the variables of interest including fatigue severity, physical activity, mood state, and HRQoL that are similar to AET+.

**Specific Aim 4:** “One-year Follow Up on Hospitalization, Lung transplant, and Mortality.” In this follow up sub-study, patients will be contacted monthly for one year after completing AET+ regarding frequency and type of exercise subjects have continued; number and nature of hospitalizations; days spent in the hospital; and the severity of their condition causing hospitalization. Subjects’ acceptance onto transplants lists and patient mortality will also be determined. We will examine potential associations among these variables and our variables of interest to determine plausibility of relationships between study outcomes and clinical endpoints.

Two corollary hypotheses will be examined: i) poor clinical outcomes are associated with the severity of cardiorespiratory impairment, and ii) AET-induced improvements in these outcomes are associated with improvements in cardiorespiratory capacity

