In Specific Aim 4, relationships between the post-study physiological variables and health outcome variables will be determined using Pearson product moment correlations and appropriate nonparametric procedures.

In all of the analyses, statistical significance will be interpreted as the probability of making a type 1 error equal to or less than 5% ( $p \leq 0.05$ ).

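### Aim 4 names only end-of-study values as predictors, so its hypothesis about improvement in cardiorespiratory capacity has no matching analysis, and the handling of death in the hospital outcomes is not stated

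*Combined protocol and SAP*

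**What the plan says.** The one-year follow-up is described in three places.

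- **Our Specific Aims (Aim 4)** sets its status: "This is a descriptive analysis to examine health outcomes of frequency, length and severity of hospitalizations", together with transplant listing and mortality.
- **Study Design and Methods, Specific Aim 4** lists the outcomes, among them "number and nature of hospitalizations; days spent in the hospital", and adds that "patient mortality will also be determined". The purpose is put broadly: "We will examine potential associations among these variables and our variables of interest to determine plausibility of relationships between study outcomes and clinical endpoints". Two hypotheses follow. The first is that "poor clinical outcomes are associated with the severity of cardiorespiratory impairment". The second is that "AET-induced improvements in these outcomes are associated with improvements in cardiorespiratory capacity".
- **Analysis** gives the whole method in one sentence: "relationships between the post-study physiological variables and health outcome variables will be determined using Pearson product moment correlations", to which the same sentence adds suitable nonparametric methods without naming them. The closing line of that section applies a 5% significance level to all analyses.

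No part of the plan names a change score or a baseline-adjusted value for Aim 4, specifies a hospitalisation measure from before training, or says how death or incomplete follow-up enters the hospital counts and days.

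**The concern.** Hypothesis ii relates one improvement to another, but the method uses a level measured once, at the end. An analyst who follows the Analysis section would report correlations that bear on hypothesis i and could be read as bearing on hypothesis ii. The protocol's own Background points to change as the quantity of interest: it cites a study in idiopathic pulmonary fibrosis in which decline in walk distance over 24 weeks predicted death at one year.

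A second gap concerns the outcome side. Hospital admissions and days are totals over a year, and a patient who dies early has less time in which to accrue them. If raw totals were correlated with capacity, that shortfall would enter the result. What is at stake is the interpretation of a descriptive aim, not the trial's main conclusion.

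**Working it through.** The plan gives no sample size, event rate or effect size for Aim 4, so there is no stated figure to reproduce.

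**1. Hypotheses against method**

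- Hypothesis i needs the severity of impairment, which is a level. The Analysis section names a level, so these match.
- Hypothesis ii needs a change in capacity, and the Analysis section names none. It also needs an improvement in hospital outcomes, which is undefined because these are recorded only from the monthly contacts after training.
- Under Study Design and Methods the control group also completes AET. No group stays untrained, so an AET-induced improvement in these outcomes cannot be shown.

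**2. How well a level stands in for change**

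Inputs: pre-post correlation r = 0.840 for walk distance in the preliminary study, and the range 0.25 to 0.40 used in the power simulations (both from Sample Size). Assumption: equal SD s before and after. No pre-post correlation is given for the Aim 2 capacity measures (AT-time, muscle oxygenation), so walk distance is a proxy.

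With D = post − pre, Cov(post, D) = s²(1 − r) and Var(D) = 2s²(1 − r). Hence corr(post, D) = √((1 − r)/2).

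| r | (1 − r)/2 = shared variance | corr(post, D) |
|---|---|---|
| 0.84 | 0.080 | 0.28 |
| 0.40 | 0.300 | 0.55 |
| 0.25 | 0.375 | 0.61 |

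With 60 completers, two-sided 5% and 80% power, the smallest detectable correlation is tanh((1.960 + 0.842)/√57) = 0.355. If the outcome depended linearly on change alone, with correlation ρ, the post value would correlate with it at ρ × corr(post, D). To reach 0.355, ρ would have to be 0.355/0.283 = 1.25 at r = 0.84, which is impossible, and 0.355/0.548 = 0.65 at r = 0.40.

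A simulation agrees (4,000 cohorts of 60; assumed overdispersed counts with mean 3 at average capacity and log-rate slope 0.6 per SD). Figures are mean Spearman correlations, with the share of cohorts at p ≤ 0.05 in brackets:

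| Outcome driven by | r | Post value | Change |
|---|---|---|---|
| Change only | 0.84 | −0.11 (13%) | −0.39 (87%) |
| Change only | 0.40 | −0.21 (38%) | −0.39 (89%) |
| Baseline only | 0.84 | −0.32 (73%) | +0.11 (14%) |
| Baseline only | 0.40 | −0.16 (22%) | +0.21 (37%) |

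At r = 0.84, the post value usually misses an effect of change and often gives a significant result when change plays no part. The last two rows show that an unadjusted change score also picks up baseline severity, which favours including baseline in the model.

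**3. Death and time at risk**

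The documents give no death or hospitalisation rate, so every figure here is illustrative. Assume cohorts of 60, hospital-day rate ratio 0.61 per SD of capacity, and death hazard ratio 0.50 or 0.30 per SD (log slopes −0.7 and −1.2).

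| One-year deaths | Pearson, raw days | Spearman, raw days |
|---|---|---|
| Full follow-up for all | about −0.38 | about −0.35 |
| 6% | −0.36 | −0.33 |
| 12 to 16% | −0.33 to −0.27 | −0.30 to −0.24 |

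Ranking does not remove the attenuation under these assumptions. The result depends, however, on hospital days accruing evenly until death. In a similar set-up (death hazard ratio 0.37), Spearman is −0.34 with full follow-up and −0.29 at 10% mortality. Adding hospital days for those who die, with an assumed mean of 2 or 5, gives −0.33 or −0.37. The bias can therefore be present, absent or slightly the other way.

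**The case against.** The strongest reply is that Aim 4 is labelled descriptive and is meant only to explore plausibility. The Methods text speaks of variables of interest without saying level or change, and the six-minute walk section defines the main outcome as a change, so change is not ruled out. This stands as far as impact goes. It does not supply an analysis: the only section that names a method names end-of-study values, walk distance is not one of the Aim 2 capacity measures, two hypotheses are explicitly to be examined, and the 5% level applies to all analyses.

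Three stronger readings are tempting, and the documents do not support them.

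- A reader might infer that the aim rests on Pearson correlation alone. The sentence goes on to allow nonparametric procedures, which are unnamed and could include a time-to-event method.
- A reader might infer that patients who die early are scored as having done well. No section says so. Mortality is collected as its own outcome, and the plan is silent on combining it with hospital use. This is a gap with a possible consequence, not a stated rule.
- A reader might infer that the association would be reversed. None of the mean correlations for hospital days in the death simulations changed sign. At 60 patients one correlation has a standard error of about 0.13 (1/√57), which is larger than most of the shifts shown.

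Ranking death as the worst outcome would not be a correction of the same quantity either. It defines a different, composite outcome, and choosing it is a matter of judgement.

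**Conclusion.** The point holds in a limited form. Hypothesis ii has no matching analysis, and that follows from the text alone. The weakness of the post value as a proxy (correlation about 0.28, or 0.55 to 0.61 at the lower pre-post correlations) rests on equal SDs and on walk distance standing in for the Aim 2 measures. Its second half, improvement in outcomes, cannot be assessed without a pre-AET measure, and the wording that credits AET has no untrained comparator behind it.

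The silence on death and time at risk is a real but secondary gap, and neither its size nor its direction can be derived from the documents. The impact is small, since the aim is descriptive and the primary 6MWD comparison is untouched.

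**What to change.** 1. In Analysis, keep level values for hypothesis i. For hypothesis ii, name the pre- to post-AET change in AT-time and muscle oxygenation as the predictor, or the post value adjusted for baseline. Adjusting for baseline is the safer choice, for the reason shown in the second simulation table.
2. State which test session supplies the pre-AET value for controls (baseline or after education), and when their follow-up year starts. The Specific Aims count from the end of the main study, while Study Design and Methods counts from the end of training.
3. Reword hypothesis ii as an association between change in capacity and outcomes over the following year, and drop the claim of AET-induced improvement in those outcomes.
4. State a method for hospital counts and days that accounts for time alive, such as a rate per time alive, or time to first hospitalisation or death.

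The capacity measurements and monthly contacts are already planned. The cost is a few sentences and a little extra analysis, with no new data.

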## Sample Size:

The broad objective of the proposed work is based on identifying effects of exercise on, and relationships among, measures of physical work capacity, fatigability, oxidative metabolism, tissue oxygen extraction, and clinical outcomes. The proposed study builds upon the PI's preliminary study of the feasibility and safety of exercise treatment for patients with ILD in which the 6MWT was the primary improvement metric. Many of the hypotheses proposed under this objective require measurement of variables not included in prior studies of the ILD population. Conversely, there are established standards for clinically relevant changes in the 6MWT and multiple studies of ILD patients with which to inform our sample size decisions and 6MWT is the primary outcome variable for the proposed study. For these reasons we will power the study on 6MWT. Specifically, changes in 6MWT distance between baseline and the second testing period are compared for ILD patients randomized to the AET+ and CON arms using a 2-way mixed model ANOVA. From this, we have determined our goal is to recruit 60 patients with ILD (30 into each group) over the duration of this study, with details below.

The prior information, assumptions, and calculation for the power analysis that was conducted are as follows. An increase in 6MWT distance of 54 to 80 m exceeds the MCID in patients with ILD. Previous studies by Holland et al. and Nishiyami et al. on exercise interventions in ILD patients have observed in post-hoc independent t-test an effect size between experimental and control groups of 0.65 and 0.86, respectively, with an increase in 6MWT distance of 31 to 42 m in the experimental group. Effect sizes in this range are associated with high-moderate to large differences.

In order to translate the existing literature's results into predictions of effect size of the 2-way mixed model ANOVA we will use as our primary statistical test, simulations were run in STATA. Simulations were drawn from normal distributions for each of control and exercise groups with equal mean and variance chosen as the average of the mean and variance observed in the control and exercise groups in Holland et al. Specifically, both groups were assumed to have mean 6MWT of 385 m and standard deviation 127 m at baseline in the simulation. The control group was assumed in all samples to show no change between baseline and retest, while different simulations were run for improvement in the exercise group of 25, 30, 35, and 40 m between baseline and retest. We did not simulate differences smaller than 25 m as this is below the MCID. At each level of improvement from treatment we simulated 3000 samples from both control and exercise groups at test-retest correlations of 0.25, 0.30, 0.35, and 0.40.

It was not possible to determine from the previously published ILD literature what level of correlation to expect between test and retest. The preliminary study performed by NIH observed a correlation of 0.840 between pre and post-treatment 6MW distances. We expect a weaker correlation between patients assigned to the CON arm of the proposed study, however, due to the conflicting effects of education and possible decline from the progression of ILD. Additionally, informal study of the plots of pre-post test change in Elia et al. also suggest the range of correlation simulated is conservative. As we are powering on only one of the multiple study aims due to the limitations of prior data and the hierarchy of study goals, we feel it prudent to risk overpowering on this outcome by using overly conservative estimates as it may ensure proper power for the other study aims.

The ranges of improvement in the treatment group and test-retest correlations considered give rise to 16 simulated data sets of 6000 observations each. Each data set was then tested with a 2-way mixed model ANOVA and the effect size recorded. Simulated effect sizes increased across the

range of correlation under consideration at each level of improvement in 6MWT distance. The observed effect sizes were 0.16-0.17 at 25 m, 0.18-0.20 at 30 m, 0.21-0.23 at 35 m, and 0.24-0.265 at 40 m. As we expect to have underestimated correlation, even at the given improvement levels the predicted effect sizes are highly conservative. With either correlation modestly above 0.40 and 30 m improvement, correlation of 0.25 and 35 m improvement, or some point in between these two at a sample size of  $n=60$  the simulated effect sizes predict a power above 80% at a significance level of 0.05. Modestly higher improvement, in the range of 35-38 m, and correlation of 0.38-0.45 will result in the study having a power of approximately 95%. This range is compatible with the observed effect sizes in the literature in the moderate to large range, using Cohen's conventions for effect sizes where these ranges are 0.25-0.4 for ANOVA and 0.5-0.8 for t-tests.

To support the results from simulation, we finish by observing how power is maintained at a slightly less conservative estimate of effect size and correlation but under the additional assumption of significant subject withdrawal from the study. Assuming an effect size of 0.25 and test-retest correlation of 0.40 then a minimum of 33 patients in each group are necessary to achieve the desired power of 0.95. Even then, if only 20 patients complete the protocol in each group post-hoc analysis predicts a not-unacceptable power of 0.803.

Our recruitment goal was therefore set at 60 patients, however, completion rates to date for this study suggest that 80 subjects may need to be consented and screened in order to achieve 60 completed subjects. Therefore, the enrollment goal remains the same at 60 patients in total (30 in each group) over the course of the study as it ensures high power for comparison of 6MWT distance between AET+ and CON groups, with a buffer for moderate patient dropout. However, recruitment will remain open until 30 subjects in each of the AET+ and CON cohorts have completed the entire protocol.

Based on this recruitment goal we have agreed upon the following strategy to maintain an effective end power. At which point we attain 45 completed subjects (total) an analysis of the standard deviations in 6MWD from pre to post will be determined in the control and intervention cohorts. To maintain the blinding controls of the study as much as possible, this analysis will be performed by our statistician only. Based on this analysis our sample size will be adjusted thereafter to reflect a more accurate sample size needed to maintain an effective end power.

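### The stated power for 6MWT distance (above 80%, about 95%) does not follow from the plan's SD of 127 m: those inputs give 13–14% and 16–19% with 30 per arm

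*Combined protocol and SAP*

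**What the plan says.** The Sample Size section powers the trial on change in 6MWT distance, AET+ against CON, by a 2-way mixed ANOVA with 30 patients per group. The simulation uses a baseline SD of 127 m in both groups, no change in controls, gains of 25, 30, 35 and 40 m with exercise, and test-retest correlations of 0.25 to 0.40.

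It reports the results as effect sizes: "The observed effect sizes were 0.16-0.17 at 25 m, 0.18-0.20 at 30 m, 0.21-0.23 at 35 m, and 0.24-0.265 at 40 m". It then claims:

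- "With either correlation modestly above 0.40 and 30 m improvement, correlation of 0.25 and 35 m improvement", or points in between: at n = 60, "the simulated effect sizes predict a power above 80% at a significance level of 0.05".
- For gains of 35–38 m, "correlation of 0.38-0.45 will result in the study having a power of approximately 95" per cent.
- "even at the given improvement levels the predicted effect sizes are highly conservative".
- "Assuming an effect size of 0.25 and test-retest correlation of 0.40 then a minimum of 33 patients in each group are necessary" for power 0.95; with 20 completers per group, "post-hoc analysis predicts a not-unacceptable power of 0.803".

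The section concludes that 60 patients give high power with some margin for withdrawals. It plans a review of the pre-to-post SDs at 45 completers, after which the sample size is adjusted.

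**The concern.** An SD of 127 m with a correlation near 0.4 implies an SD of change near 139 m. A 30 m difference is then about a fifth of an SD, and 30 per arm cannot detect that with 80% power.

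This is the primary outcome. The choice of 60 completers, the description of the assumptions as conservative and the claimed margin for withdrawals all rest on these figures. If power is much lower than stated, a non-significant result could be misread as evidence that exercise training does not work. The same route from metres to effect size could also carry over into the SD review.

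**Working it through.** **Inputs from the plan (Sample Size):** SD 127 m, control change 0, 30 per arm, significance level 0.05, and the gains and correlations in its claims.

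**Assumptions made here:** two-sided test; retest SD also 127 m; r = 0.42 for a correlation modestly above 0.40 (r from 0.40 to 0.45 gives 13.0–13.8% at 30 m).

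**1. The plan's supporting figures.** For the group-by-time interaction with two time points, use noncentrality λ = f² × N × 2/(1 − r), with F on 1 and N − 2 degrees of freedom. With f = 0.25 and r = 0.40:

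- N = 66: λ = 0.0625 × 66 × 2/0.60 = 13.75, power 0.955. N = 64 gives 0.949, so 33 per group is right.
- N = 40: λ = 8.33, power 0.803, as stated.

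Both figures are correct for that f and r.

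**2. The main claims by the same route, N = 60, taking the reported effect sizes as f:**

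- f = 0.20, r = 0.42: 0.808. This reproduces.
- f = 0.21, r = 0.25: 0.743. This is not above 80%.
- f = 0.23, r = 0.38: 0.882. f = 0.25 (interpolated here for 38 m), r = 0.45: 0.953.

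So one of the two 80% scenarios fails even on the reported values.

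**3. From metres to f.** In a 2 × 2 layout a between-arm difference in change of δ gives interaction effects of ±δ/4 in each cell, so in this formula f = δ/(4 × 127). Then 30 m is 0.059, 35 m is 0.069, 38 m is 0.075 and 40 m is 0.079. The reported values are about three times larger. An f of 0.25 corresponds to 0.25 × 508 = 127 m.

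**4. Power from the stated inputs.** With two groups and two times, the interaction test is a t-test on change scores. SD of change = 127 × √(2(1 − r)); noncentrality = δ/(SD × √(2/30)); 58 degrees of freedom. For 30 m and r = 0.42, SD = 127 × √1.16 = 136.8 m and noncentrality = 30/(136.8 × 0.258) = 0.85.

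| Gain, r | SD of change (m) | Power | Plan states | Lowest possible SD (m) | Power there |
|---|---|---|---|---|---|
| 30 m, 0.42 | 136.8 | 13% | above 80% | 115.3 | 17% |
| 35 m, 0.25 | 155.5 | 14% | above 80% | 123.0 | 19% |
| 35 m, 0.38 | 141.4 | 16% | about 95% | 117.5 | 21% |
| 38 m, 0.45 | 133.2 | 19% | about 95% | 113.4 | 25% |

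The lowest possible SD is 127 × √(1 − r²), the minimum over all retest SDs. Simulation of 40,000 trials per scenario gave 13.4%, 14.0%, 15.7% and 19.5%. Putting the f values from step 3 into the step 1 formula returns the same powers as the t-test.

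**5. Other readings.**

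- The pilot correlation of 0.840 gives an SD of change of 71.8 m and power of 36% for 30 m.
- The reported effect sizes already rise with r. If r is not applied again, 0.20–0.21 gives 12–13% as a standardised difference in change, or 33–36% as an ANOVA f that already contains r.
- A 40 m gain at r = 0.40 (SD 139.1 m) gives 21% with 33 per group and 14% with 20.

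**The case against.** - **The claims rest on the recorded effect sizes, not on metres.** This is partly right: f = 0.20 with r = 0.42 gives 0.808, and 33 per group and 0.803 both reproduce. The fault is therefore confined to one step, but the power statements are worded in metres and correlation and fail in those terms.
- **The test could be one-sided**, since only 0.05 is stated and hypothesis 1.1 is directional. One-sided power is 21–29%, and at most 26–36% for any retest SD, still far from 80%.
- **The inputs were deliberately pessimistic.** The plan says so, and the published effect sizes it cites (0.65 and 0.86), if they are between-arm standardised differences in change, give about 70% and 91% with 30 per arm. But the plan claims high power at correlations and gains in or just beyond its simulated range, and never reconciles the published values with an SD of 127 m.
- **The cause is not proven.** It looks as though standardised differences in change were entered as f, so that r is counted twice. Those differences would be 0.193–0.216 at 30 m, and the reported values run about 7–9% lower. The metric and code are not shown, so this remains an inference; the error does not depend on it.
- **The review at 45 completers could correct the size.** That stands as mitigation. However, it names no target difference and no target power, and the section uses both 80% and 0.95. It does not make the stated figures right.

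**Conclusion.** The concern holds. Under the plan's own SD, correlations and gains, 30 per arm gives 13–14% power where above 80% is stated and 16–19% where about 95% is stated. This assumes a two-sided 5% test and a retest SD of 127 m; relaxing the retest SD gives at most 17–25%. The supporting figures of 33 per group and 0.803 are arithmetically correct, but for an effect that equals 127 m on the plan's SD.

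These are powers under the stated inputs, not the trial's true power. With 30 per arm and a 30 m difference, 80% is reached only if the SD of change is about 41 m or less, and 95% only at about 32 m or less. The plan gives no SD of change. The statements need correcting because the sample size for the primary outcome is justified by them.

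**What to change.** In the Sample Size section:

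1. Withdraw or restate the 80% and 95% power claims, the description of the effect sizes as conservative, and the conclusion of high power with a margin for withdrawals.
2. Keep 33 per group and 0.803 only as conditional on f = 0.25 and r = 0.40, and say what that f means in metres.
3. State the SD of change relied on and why. Show power for a 30 m between-arm difference with 30 completers per arm over illustrative SDs of change:

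| SD of change (m) | 36 | 48 | 65 | 72 | 139 |
|---|---|---|---|---|---|
| Power | 89% | 66% | 42% | 36% | 13% |

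4. For the review at 45 completers, state the target difference (30 m in hypothesis 1.1) and one target power, settling 80% against 0.95. Compute n per arm = 2 × (1.96 + z)² × SD²/30², with z = 0.84 for 80% or 1.645 for 95%. Use the pooled within-arm SD of change, or the residual SD if ANCOVA is the analysis, without going through f. At SD 48 m: 2 × 2.80² × 2304/900 = 40.1, so 41 per arm for 80%; 2 × 3.605² × 2304/900 = 66.5, so 67 for 95%. The exact t calculation gives 42 and 68.

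The cost is protocol wording and one recalculation. The stated power becomes less favourable, and the review would call for more than 30 per arm if the SD of change exceeds about 41 m (80%) or 32 m (95%).
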